13. REGULATORY CONSIDERATIONS

13.1 Protocol Review and Amendments

This protocol, the proposed informed consent and all forms of participant information related to the study (e.g., advertisements used to recruit participants) and any other necessary documents must be submitted, reviewed and approved by a properly constituted IRB governing each study location.

Any changes made to the protocol must be submitted as amendments and must be approved by the IRB prior to implementation. Any changes in study conduct must be reported to the IRB. The Overall Principal Investigator (or Protocol Chair) will disseminate protocol amendment information to all participating investigators.

All decisions of the IRB concerning the conduct of the study must be made in writing.

13.2 Informed Consent

All participants must be provided a consent form describing this study and providing sufficient information for participants to make an informed decision about their participation in this study. The formal consent of a participant, using the IRB approved consent form, must be obtained before the participant is involved in any study-related procedure. The consent form must be signed and dated by the participant or the participant's legally authorized representative, and by the person obtaining the consent. The participant must be given a copy of the signed and dated consent document. The original signed copy of the consent document must be retained in the medical record or research file.

CONFIDENTIAL

This document is confidential. Do not disclose or use except as authorized.

13.3 Ethics and Good Clinical Practice (GCP)

This study is to be conducted according to the following considerations, which represent good and sound research practice:

- E6 Good Clinical Practice: Consolidated Guidance
www.fda.gov/downloads/RegulatoryInformation/Guidances/UCM129515.pdf
link does not work, error message
- US Code of Federal Regulations (CFR) governing clinical study conduct and ethical principles that have their origin in the Declaration of Helsinki
 - Title 21 Part 11 – Electronic Records; Electronic Signatures
www.access.gpo.gov/nara/cfr/waisidx_02/21cfr11_02.html
 - Title 21 Part 50 – Protection of Human Subjects
www.access.gpo.gov/nara/cfr/waisidx_02/21cfr50_02.html
 - Title 21 Part 54 – Financial Disclosure by Clinical Investigators
www.access.gpo.gov/nara/cfr/waisidx_02/21cfr54_02.html
 - Title 21 Part 56 – Institutional Review Boards
www.access.gpo.gov/nara/cfr/waisidx_02/21cfr56_02.html
 - Title 21 Part 312 – Investigational New Drug Application
www.access.gpo.gov/nara/cfr/waisidx_02/21cfr312_02.html
- State laws

It is understood that deviations from the protocol should be avoided, except when necessary to eliminate an immediate hazard to a research participant. In such case, the deviation must be reported to the IRB according to the local reporting policy.

13.4 Study Documentation

The investigator must prepare and maintain adequate and accurate case histories designed to record all observations and other data pertinent to the study for each research participant. This information enables the study to be fully documented and the study data to be subsequently verified.

Original source documents supporting entries in the case report forms include but are not limited to hospital records, clinical charts, laboratory and pharmacy records, recorded data from automated instruments, microfiches, photographic negatives, microfilm or magnetic media, and/or x-rays.

13.5 Records Retention

CONFIDENTIAL

This document is confidential. Do not disclose or use except as authorized.

All study-related documents must be retained for the maximum period required by applicable federal regulations and guidelines or institutional policies.

13.6 Data Collection

Data will be collected and reported on either paper case report forms (CRF) or through an internal data monitoring system, which will be determined prior to the start of the study.

CONFIDENTIAL

This document is confidential. Do not disclose or use except as authorized.

14. STATISTICAL CONSIDERATIONS

The hypothesis of this study is that SGI-110, a demethylating agent, will lead to at least a 25% response rate in any one or more of the following response assessments: IWG-MDS, IWG-MF criteria or MF-SAF scores. Based on historical data, there is approximately a 10% hematological response rate with standard therapies and there is no precedent for quality of life response with any current therapy

14.1 Study Design/Endpoints

This is an open-label, single-arm phase II study designed to explore the clinical activity of SGI-110, a demethylating agent, in patients with MPN. The hypothesis of this study is that SGI-110 will lead to at least a 25% response rate in any one or more of the following response assessments: IWG-MDS, IWG-MF criteria, or MF-SAF scores. Based on historical data, there is approximately a 10% hematological response rate with standard therapies and there is no precedent for quality of life response with any current therapy.

Sample size considerations:

This is a phase II trial with 50 patients in the study arm; a 95% confidence interval for the hematological response rate can be constructed to be within $\pm 12.0\%$ of the observed response rate. This calculation assumes a hematological response rate of 25%. The primary endpoint is the hematological response proportion, as measured by any one or more of the following response assessments: IWG-MDS, IWG-MF criteria or MF-SAF scores. Based on historical data, the hematological response proportion based on standard therapies is approximately 10%. Sample size recommendations for the current design are determined according to A'Hern's exact single-stage phase II design (A'Hern, RP, 2001). We project a hematological response proportion of 10%, below which the regimen will be unacceptable, and a hematological response proportion of 25%, above which the regimen will be considered worthy of further exploration. The null hypothesis that the hematological response proportion is less than or equal to 10% will be tested against the alternative hypothesis that the hematological response proportion is greater than or equal to 25%. The sample size computations were performed assuming a 5% level of significance and 85% power. Patients will be continuously accrued throughout the study up to a maximum of 47 patients. The new regimen will be declared effective and worthy of further testing if 9 or more patients respond among the 47 patients entered into the study. This exact single-stage design yields a ≥ 0.85 probability of a positive result if the true hematological response proportion is $\geq 25\%$. It yields a ≥ 0.95 probability of a negative result if the true hematological response proportion is $\leq 10\%$. A one-sided 95% confidence interval constructed around the expected hematological response proportion of 25% will extend 10.4% from the observed hematological response proportion. Assuming that approximately 5% of patients will be unevaluable/ineligible, we anticipate that a total of 50 patients will be enrolled in the study (Reference: A'Hern AP. Sample size tables for exact single-stage phase II designs. Statistics in Medicine 2001;20:859-866.)

Analysis Plan:

CONFIDENTIAL

This document is confidential. Do not disclose or use except as authorized.

The primary endpoint of the hematological response proportion will be calculated and a 95% confidence interval will be estimated via binomial proportions. Descriptive statistics will be utilized to describe the parameter proportion defined above (i.e., frequency, percent). Estimated differences in the hematological response proportion between categories of demographic and treatment variables of interest (evaluated by the two-sample t-test, Wilcoxon rank-sum test, Fisher's exact test, and chi-square test, as appropriate) will serve as preliminary data (i.e., hypothesis-generating) for future studies. Similar analyses will be conducted for secondary outcomes of quality of life. Exploratory analyses of the hematological response rate and quality of life outcomes will be also be stratified by specific cytogenetic and/or molecular subgroups of MPN.

All p-values will be one-sided with statistical significance evaluated at the 0.05 alpha level. One-sided ninety-five percent confidence intervals will be calculated to assess the precision of the obtained estimates. All analyses will be performed in SAS Version 9.3 (SAS Institute, Inc., Cary, NC) and Stata Version 13.0 (StataCorp, College Station, TX).

Safety Analyses:

The frequency of subjects experiencing toxicities will be tabulated. Toxicities will be assessed and graded according to CTCAE v. 4.0 terminology. Exact 95% confidence intervals around the toxicity proportions will be calculated to assess the precision of the obtained estimates.

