1. OBJECTIVES

- 1.1 **Study Design:** Open label single-arm, single-institution study to evaluate the efficacy and safety of SGI-110 in Philadelphia chromosome negative (Ph-) Myeloproliferative Neoplasms (excluding PV, ET and primary/secondary myelofibrosis). While this study would begin as a single institution study, it may be open later as a multi institutional study.
- 1.2 **Primary Objective:** Determine the efficacy of SGI-110 in improving hematological and/or quality of life outcomes in patients with Ph- MPN

1.3 **Secondary Objectives:**

Determine whether SGI-110 has increased efficacy in specific morphologic, cytogenetic and/or molecular subgroups of MPN

Perform correlative scientific studies to assess potential epigenetic or other biomarkers predictive of response

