2.5 Rationale

2.5.1 Both decitabine and SGI-110 have demonstrated safety and efficacy in patients with MDS, AML and CMML. Based on these data, substantial clinical experience and the lack of an effective treatment option in PHN-MPN, we hypothesize that treatment with SGI-110 will result in improved hematological and quality of life outcomes in patients with these diseases. SGI-110 will be administered subcutaneously at the dose level of 60mg/m² for 5 days to be repeated every 28 days. If the treating physician feels that SGI-110 needs to be started before 28 days for subsequent cycles, SGI-110 can be started before the 28 days in those clinical situations after getting permission from the study PI. To capture the potential ability of SGI-110 to improve both hematological and QOL measures, we will utilize a recently published composite endpoint for response assessment based on IWG-MDS, IWG-myelofibrosis and MFSAF (Myeloproliferative Neoplasm Symptom Assessment Form) tools: Savona et al., An international consortium proposal of uniform response criteria for myelodysplastic/myeloproliferative neoplasms (MDS/MPN) in adults. *Blood*, 125(12):1857-65.

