14.2 Reporting and Exclusions

14.2.1 Evaluation of toxicity. All participants will be evaluable for toxicity from the time of their first treatment.

14.2.2 Evaluation of response. All participants included in the study must be assessed for response to treatment. Each participant should be assigned one of the following categories: 1) complete response, 2) partial response, 3) stable disease, 4) progressive disease, 5) early death from malignant disease, 6) early death from toxicity, 7) early death because of other cause, or 9) unknown (not assessable, insufficient data). By arbitrary convention, category 9 usually designates the "unknown" status of any type of data in a clinical database.

CONFIDENTIAL

This document is confidential. Do not disclose or use except as authorized.

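### The primary endpoint is called hematological response but can be met by a symptom score alone, and its 10% null is given only as a hematological rate

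*Combined protocol and SAP*

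**What the plan says.** The primary endpoint in 14.1 (sample size considerations) is the "hematological response proportion, as measured by any one or more of the following response assessments: IWG-MDS, IWG-MF criteria or MF-SAF scores". The MF-SAF, reproduced in section 10, is a patient-completed symptom form. A composite of this kind agrees with three other places:

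- Objective 1.2: "Determine the efficacy of SGI-110 in improving hematological and/or quality of life outcomes in patients with Ph- MPN".
- Section 2.5.1, which aims to capture the drug's ability "to improve both hematological and QOL measures, we will utilize a recently published composite endpoint for response assessment".
- The hypothesis opening section 14 and repeated in 14.1, which sets the 25% target on any one or more of the three assessments.

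Two places sit less easily with it. After naming the hematological response proportion as primary, the analysis plan in 14.1 adds: "Similar analyses will be conducted for secondary outcomes of quality of life". Section 14.2.2 says: "Each participant should be assigned one of the following categories: 1) complete response, 2) partial response, 3) stable disease, 4) progressive disease", followed by three kinds of early death and an unknown category.

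The source of the null is given for hematological response only: "Based on historical data, the hematological response proportion based on standard therapies is approximately 10" percent. For symptoms the text says that "there is no precedent for quality of life response with any current therapy" and gives no rate. The design property is worded in the same term: "It yields a ≥ 0.95 probability of a negative result if the true hematological response proportion is" 10% or less.

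**The concern.** The name of the endpoint and the source of its null point to hematological response, while the definition admits a symptom response on its own. Two analysts following the plan could classify the same patient differently, and around the cutoff of 9 that can reverse the conclusion.

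If symptom-only responders count, the trial can report a positive hematological response proportion with fewer than 9 hematological responders. A self-reported score in an open-label, single-arm trial can improve for reasons unrelated to the drug, and the lack of precedent with other therapies puts no upper limit on that. The futility rule in 12.1.2 relies on the protocol's own definition of response, so it has the same ambiguity. If symptom-only responders do not count, the definition in 14.1 is wrong and the test leaves out the quality-of-life part of objective 1.2.

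**Working it through.** **Inputs from 14.1:** n = 47, a go if 9 or more respond, null 10%, alternative 25%, 5% significance (one-sided), 85% power.

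**Formula:** P(go | p) = Σ from k = 9 to 47 of C(47,k) p^k (1−p)^(47−k), where p is the rate of whatever is counted as a response.

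**The plan's own figures.** P(go | 0.10) = 0.0411, so the probability of a negative result is 1 − 0.0411 = 0.9589. P(go | 0.25) = 0.8649. Both meet the stated 0.95 and 0.85. The smallest exact single-stage design meeting these limits is n = 47 with cutoff 9, and 47/0.95 = 49.5 gives the 50 to be enrolled. The arithmetic is right; the question is which p it applies to.

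**Margin.** Solving P(go | p) = 0.05 gives p = 0.1037. The 0.95 property therefore holds only while the counted rate is at most about 10.4%.

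**Adding symptom-only responders.** Let h be the hematological rate and s the proportion responding on the symptom form only. The groups do not overlap, so p = h + s. The documents give no value for s; those below are assumptions.

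| h | s | Counted rate p | P(go) |
|---|---|---|---|
| 10% | 0 | 10% | 4.1% |
| 10% | 1% | 11% | 6.8% |
| 10% | 2% | 12% | 10.4% |
| 10% | 5% | 15% | 26.7% |
| 8% | 2% | 10% | 4.1% |
| 8% | 3% | 11% | 6.8% |
| 5% | 5% | 10% | 4.1% |

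The room for symptom-only response is 10.37 − 10 = 0.37 points at h = 10%, 2.37 points at 8% and 5.37 points at 5%.

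**A go with fewer than 9 hematological responders.** At h = 10%, sum over k = 0 to 8 the product Bin(k; 47, 0.10) × P(Bin(47 − k, s/0.9) ≥ 9 − k). This gives 2.7% at s = 1%, 6.3% at 2% and 22.5% at 5%.

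**What such a go shows about hematological response.** The exact one-sided 95% lower bound for 8 of 47 is 8.8% (p = 0.093 against 10%), which does not exclude 10%. For 9 of 47 it is 10.4% (p = 0.041), which does.

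**Futility rule (12.1.2).** Fewer than 10% responses means 2 or fewer, whether 25 or 30 patients are assessed (the section sets 25 as a minimum). At h = 10% with s = 0, 2% and 5%, the stop probability is 53.7%, 40.9% and 25.4% at 25 patients, and 41.1%, 28.5% and 15.1% at 30.

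**The case against.** The strongest reply is that 14.1 uses the hematological response proportion as a defined term, meaning the any-of-three composite, and states its error rates in that term. Objective 1.2, section 2.5.1 and the hypothesis in section 14 all support this. Read so, the 0.95 statement is true. A drug with 10% hematological response plus genuine symptom responders is then not a null drug, and a go for it is not a false positive. This stands, and it limits the point to a misnamed endpoint with a weakly supported null.

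The plan also gives some basis for the composite null: about 10% hematological response, with no precedent for quality-of-life response, so nothing is added. That basis is thin, because no precedent is not a rate, but it is stated.

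Two inferences go too far:

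- A reader might take 14.2.2 as excluding symptom responses. It does not mention quality of life, and it lacks every clinical-benefit category of 10.1.1, including erythroid, platelet and neutrophil response. It leaves symptom improvement and hematological improvement short of complete or partial response equally without a place.
- A reader might take the secondary listing of quality of life as removing it from the primary endpoint. A scale can feed a responder composite and also be analysed separately; the text does not say which is meant.

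Section 10.1.1 would restrict symptom response (no progression, a decrease of at least half, a minimum starting score). It is written for the MPN-SAF TSS, however, whereas 14.1 and the study calendar name the MF-SAF, and section 14 does not say that those limits apply.

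**Conclusion.** The point holds as an unresolved endpoint definition with a null that describes only part of what is counted. Under the composite reading, the 0.95 statement is formally true and its 10% null is thinly supported. Under the hematological reading, it fails once the counted rate passes about 10.4%. In both cases the plan, followed as written, can deliver a positive result labelled hematological with 8 or fewer hematological responders.

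The size depends on an assumed symptom-only rate. At 10% hematological response, P(go) rises from 4.1% to 10.4% with 2 points and to 26.7% with 5 points; it does not rise above 4.1% when the total is 10% or less. These figures leave out the futility stop.

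A reader might infer that the trial has lost control of its error rate, or that the composite null must be raised. The documents support neither: they give no symptom-only rate and no basis for another null, and the design calculation is correct for a counted rate of 10%. Nor is the 9-of-47 rule the only decision rule, since 12.1.2 has a futility stop.

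**What to change.** 1. Reconcile the endpoint definition and the analysis plan in 14.1 with the category list in 14.2.2, so that they say whether a symptom-only response counts and where clinical-benefit responses are recorded.
2. Use the same definition in the futility rule of 12.1.2.
3. State the 0.95 and 0.85 properties for the endpoint actually tested. If the composite is kept, give the reason for 10% as its null.
4. Whichever endpoint is kept, report the hematological-only responder count with its exact confidence interval against 10%, and the symptom-only count separately.
5. Do not describe a go that depends on symptom-only responders as evidence that hematological response exceeds 10%.

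The cost is text and a little more analysis, with no new procedures. If the composite is kept, a go may carry a weaker hematological claim. If symptom-only responses are excluded, the test no longer covers the quality-of-life part of objective 1.2. The 86.5% power then requires a hematological rate of 25% by itself; it is 73.5% at 22% and 61.6% at 20%. Changing the null, cutoff or sample size is a separate trade-off and is not needed to resolve this point.

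### One-sided 0.05 p-values and one-sided 95% intervals are prescribed for every analysis, but only the primary test has a stated direction (minor)

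*Combined protocol and SAP*

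**What the plan says.** The rule is in the Analysis Plan part of section 14.1: "All p-values will be one-sided with statistical significance evaluated at the 0.05 alpha level". The next sentence asks for one-sided 95% confidence intervals to show precision. No analysis is exempted from either.

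The paragraph before it lists what the rule must cover:
- "Estimated differences in the hematological response proportion between categories of demographic and treatment variables of interest", to be assessed by t-test, Wilcoxon rank-sum, Fisher's exact or chi-square test as suits the variable, and described as hypothesis-generating;
- similar analyses for quality of life;
- exploratory analyses of response and quality of life by cytogenetic or molecular subgroup.

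The subgroup work serves a secondary objective in section 1.3: "Determine whether SGI-110 has increased efficacy in specific morphologic, cytogenetic and/or molecular subgroups of MPN". That objective does not say which subgroup is expected to do better.

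Only the primary test has a direction. The sample size text in section 14.1 sets the lower mark: "We project a hematological response proportion of 10%, below which the regimen will be unacceptable". The upper mark, from which the drug would merit more study, is 25%.

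**The concern.** A one-sided p-value has no meaning until a direction is named. The plan names one for the primary test and for nothing else. For the other comparisons the analyst must do one of three things: fix a direction that the plan does not give, take the direction from the data, or depart from the rule. Taking it from the data turns a nominal 5% test into a nominal 10% test, while the report still describes it as 5%.

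With more than two unordered categories the rule cannot be followed, because an overall chi-square or Fisher test has no tail to choose. Section 3.1.1 admits six disease types, so the morphologic part of the secondary objective could easily lead to such a table.

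The intervals have the same difficulty. For a subgroup difference with no expected direction, it is unclear which bound to report, and the other side is left open.

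At stake is how far the reader can trust the p-values behind a secondary objective and the preliminary data offered for future studies. The trial's main conclusion is not at stake.

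**Working it through.** **1. The primary design, where one-sided testing fits.** Inputs from section 14.1: null 10%, alternative 25%, "The sample size computations were performed assuming a 5% level of significance and 85% power", and success if "9 or more patients respond among the 47 patients entered into the study".
- Error: P(X ≥ 9 | n = 47, p = 0.10) = 0.0411, below 0.05.
- Power: P(X ≥ 9 | n = 47, p = 0.25) = 0.8649, above 0.85.
- A search over n confirms that 47 with a cut-off of 9 is the smallest design that meets both limits.
- Enrolment ("Assuming that approximately 5% of patients will be unevaluable/ineligible"): 47 / 0.95 = 49.5, rounded up to 50.

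The plan's figures are reproduced, and they correspond to a one-sided 0.05 test.

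**2. Nominal error of an undirected comparison.** For a symmetric test statistic with one-sided critical value z(0.95):
- direction fixed in advance: 1 − Φ(z(0.95)) = 0.05;
- direction taken from the data: 2 × [1 − Φ(z(0.95))] = 0.10;
- two-sided test at 0.05, with 0.025 per tail: 0.05.

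**3. Exact error at this trial's size.** The documents give no group sizes and no common response rate for these comparisons. The splits and rates below are therefore assumptions. For each case, every possible 2×2 table was weighted by its binomial probability under equal response in the two groups. The weights of the tables declared significant were then added up.

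| Split, common rate | Test | Direction fixed in advance, 0.05 | Direction from data, 0.05 | Two-sided 0.05 |
|---|---|---|---|---|
| 24 v 23, 25% | pooled chi-square | 0.048 | 0.101 | 0.050 |
| 30 v 17, 25% | pooled chi-square | 0.044 | 0.104 | 0.048 |
| 25 v 25, 25% | pooled chi-square | 0.050 | 0.100 | 0.054 |
| 24 v 23, 10% | pooled chi-square | 0.060 | 0.110 | 0.046 |
| 24 v 23, 25% | Fisher | 0.024 | 0.050 | 0.037 |
| 30 v 17, 25% | Fisher | 0.021 | 0.047 | 0.031 |
| 25 v 25, 25% | Fisher | 0.027 | 0.054 | 0.022 |
| 24 v 23, 10% | Fisher | 0.010 | 0.030 | 0.030 |

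With the pooled chi-square test (here the pooled z statistic, whose square is chi-square), a direction taken from the data gives 0.100 to 0.110, against 0.046 to 0.054 for the two-sided test. With Fisher's exact test it gives 0.030 to 0.054, against 0.022 to 0.037. Its ratio to the two-sided error runs from about 1.0 (0.030 / 0.030) to about 2.5 (0.054 / 0.022).

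**4. Intervals.** The ±12.0% in section 14.1 is a two-sided figure: 1.96 × √(0.25 × 0.75 / 50) = 0.120. The 10.4% given there is one-sided: 1.645 × √(0.25 × 0.75 / 47) = 0.104. The plan therefore already uses two-sided precision for the primary rate, and two-sided intervals elsewhere would not be foreign to it.

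**The case against.** The strongest reply is that the plan limits the consequence itself. It calls the category comparisons hypothesis-generating and the subgroup analyses exploratory, and no decision rule uses them. A lenient screening level in a single-arm phase II trial is partly a matter of preference. A reader with the reported counts could also compute a two-sided p-value. This stands, and it is why the point is minor. It does not remove the point, because the plan itself attaches a significance threshold to these analyses and one of them answers a stated objective.

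A reader might infer that the rule doubles the false-positive rate of all these comparisons. The documents do not support that. Nothing says that directions will be read from the data, and a direction fixed in advance keeps the nominal level at 5%. Even with a data-chosen direction, the increase depends on the test. Fisher's exact test, one of the four listed, stayed at or below 0.054 in the cases tabulated.

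A reader might also work out the chance of at least one false positive over ten comparisons: 1 − 0.90^10 = 0.651, against 1 − 0.95^10 = 0.401 with two-sided tests. The plan gives no number of comparisons, and comparisons made on the same 47 or so patients are unlikely to be independent. The 0.401 would also remain after the change. It reflects multiplicity, which two-sided testing does not address.

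Finally, the rule is not unworkable everywhere. The t-test, the Wilcoxon test and a 2×2 Fisher test all have one-sided forms once a direction is named. Only tables with more than two unordered categories have none.

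**Conclusion.** The point holds and is minor. The plan applies one-sided p-values and one-sided intervals to every analysis but states a direction for the primary test alone. Elsewhere the rule is undefined until a direction is supplied, and for an overall test over more than two unordered categories it has no form at all. That much follows from the text and needs no assumption.

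The numerical effect is conditional. If the direction is taken from the data, the nominal error per comparison goes from 5% to 10%. The exact figures rest on the assumed splits and rates, and they show about that increase for the pooled chi-square test but not for Fisher's exact test. The documents do not support a flat claim of doubling or any family-wise percentage. The rule of 9 or more responders among 47, with its error of 0.0411 and power of 0.8649, is unaffected.

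**What to change.** Replace the blanket sentence in the Analysis Plan of section 14.1. Keep the one-sided 0.05 level for the primary test against 10%. For all category, cytogenetic or molecular subgroup and quality-of-life comparisons, report two-sided p-values and two-sided 95% intervals. If the sponsor wants a one-sided test for a particular comparison, its direction should be written down before analysis.

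The cost is one or two sentences. The 47 evaluable patients, the cut-off of 9 and the enrolment of 50 do not change. The downside is that exploratory p-values become less favourable, so fewer of them will fall below 0.05.
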